#### 4. INTRODUCTION

#### 4.1. Study Overview

This is a Phase 2 safety, tolerability, and efficacy study of XT-150 in adult participants with pain due to osteoarthritis of the knee. The study will be conducted in 2 Stages, A and B.

Stage A is placebo controlled for six months following intra-articular injection in the Index Knee, which is defined by Kellgren-Lawrence grading and participant-reported pain. The primary efficacy endpoint is 30% response rate in WOMAC pain at Day 180.

Stage B continues for an additional six months of safety and efficacy monitoring during which participants can elect for a second injection to the Index Knee. Active 150  $\mu g$  or 450  $\mu g$  XT-150 will be randomly chosen for the second injection.

At six months of exposure, after a single injection dose, the double blinded, placebo-controlled portion of this randomized RCT will end, and an analysis described below will be performed of both efficacy and safety. Subjects continue in the study in a blinded fashion for an additional six months of follow-up. During the second 6-month period, subjects may request a second injection, which will be 450  $\mu$ g or 150  $\mu$ g (this second dose having been randomized previously as described in the treatment dose sequence, section 4.3).

#### 4.2. Study Objectives

Safety:

• To confirm the safety and tolerability of intra-articularly-injected XT-150

Efficacy:

CONFIDENTIAL Page 7 of 27

Protocol No.: XT-150-2-0204 Sponsor: Xalud Therapeutics, Inc.

To establish analgesic efficacy of intra-articularly-injected XT-150

#### 4.3. Study Design

Participants will provide informed consent and meet all study eligibility criteria before any study procedures are initiated. Baseline confirmation of study eligibility will be completed the day before or day of study drug administration. The Index Knee for study drug injection will be the OA-affected joint identified by Kellgren-Lawrence grade of 2 or 3; and WOMAC Pain Subscale  $\geq 8$  on a scale of 20.

Study drug will be administered by intra-articular (IA) injection into the joint space of the Index Knee.

Participants will undergo the study in 2 stages, A and B, over a 12-month period:

Stage A: Placebo-controlled for 6 months

Stage B: Continued follow up for 6 months with the option of randomly receiving a single 150  $\mu$ g or 450  $\mu$ g injection as the second injection to the Index Knee (knee dosed in Stage A)

In Stage A (6 months duration), about 270 participants will be randomly enrolled into 1 of 6 treatment groups at dose levels (approximately 90 participants/ dose level) to receive a 1 mL single injection containing 150  $\mu$ g XT-150, 450  $\mu$ g XT-150, or placebo on Day 0.

In Stage B (further 6 months duration), participants will have continued follow up for 6 months with the option of receiving a pre-randomized at study start single 150  $\mu$ g or 450  $\mu$ g injection as the second injection (1 mL) to the Index Knee (knee dosed in Stage A) at any time up to Day 330.

Safety parameters and efficacy endpoints for each participant will be evaluated monthly from the first XT-150 dose (Stage A, Day 0) for about 1 year (end of Stage B, Day 360).

#### 4.4. Study Treatment

Treatments in Stage A:

- Placebo (1 mL phosphate-buffered saline for injection)
- 150 μg XT-150 (1 mL)
- 450 μg XT-150 (1 mL)

Treatments in Stage B:

- 150 μg XT-150 (1 mL)
- 450 μg XT-150 (1 mL)

At enrolment in Stage A, participants will be randomly enrolled into 1 of 6 treatment sequences (approximately 45 participants/ group) to receive one of 3 treatments in Stage A, and, optionally, one of 2 treatments in Stage B.

CONFIDENTIAL Page 8 of 27

Final 2.0, 11 Oct 2021

Protocol No.: XT-150-2-0204 Sponsor: Xalud Therapeutics, Inc.

At any time in Stage B up to Day 330, inclusive, participants can elect for a single injection to the knee dosed in Stage A (Index Knee). The second injection dose will be either 150  $\mu$ g or 450  $\mu$ g XT-150, according to the randomized treatment sequence allocated on enrolment in Stage A. There will be no placebo comparator in Stage B.

Treatment sequences for randomization:

- XT-150 (150 μg) in Stage A, followed by XT-150 (150 μg) in Stage B
- XT-150 (150 μg) in Stage A, followed by XT-150 (450 μg) in Stage B
- XT-150 (450 μg) in Stage A, followed by XT-150 (150 μg) in Stage B
- XT-150 (450 μg) in Stage A, followed by XT-150 (450 μg) in Stage B
- Placebo in Stage A, followed by XT-150 (150 μg) in Stage B
- Placebo in Stage A, followed by XT-150 (450 μg) in Stage B

#### 4.5. Sample Size

A total of 270 subjects will be randomized to receive one of 6 treatment sequences in a 1:1:1:1:11 ratio. This will result in subjects randomly receiving one of the three treatments in Stage A in a 1:1:1 ratio The sample size of 90 subjects per treatment in Stage A provides more than 90% power to detect a greater responder rate in at least one XT-150 group compared to placebo and 85% power to detect both arms superior to placebo, assuming the WOMAC Pain Score at Day 180 responder rate is 30% in each XT-150 group and 10% in the placebo group.

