13.1 Determination of Sample Size

A total of 270 subjects will be randomized to the 3 treatment groups in a 1:1:1 ratio. The sample size of 90 subjects per group provides more than 90% power to detect a greater responder rate in at least one XT-150 group compared to placebo and 85% power to detect both arms superior to placebo, assuming the responder rate is 30% in each XT-150 group and 10% in the placebo group. As a sensitivity analysis of different assumptions on the response rates in the placebo and XT-150 groups, Table 7 shows the statistical power to detect that at least one treatment group provides greater response than placebo and to detect that both treatment groups provide greater responses.

		Statistical Power (%)				
Placebo response rate (%)	XT-150 response rate (%) in both treatment arms	To detect at least one treatment arm superior to placebo	To detect both treatment arms superior to placebo			
10	25	78	57			
	30	95	85			
	35	99	97			
15	25	38	18			
	30	70	46			
	35	91	77			

Table 7. Treatment Effect That Can Be Detected

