13.5.1 Multiplicity of endpoints

The statistical analysis of the primary endpoint will preserve a familywise error rate of 0.025 (one-sided), accounting for statistical tests of each of the two XT-150 doses to placebo with respect to the primary endpoint.

[figure not shown]
P-values from analyses of other endpoints may be interpreted as descriptive statistics.

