13.5.2 Statistical methods for the binary outcomes

Whether the subject achieves at least a 30% improvement from baseline in WOMAC Pain Score at Day 180 will be coded as a binary outcome: responder or non-responder. Subjects who withdraw from study before Day 180 or otherwise do not provide a response at that time point will be considered non-responders. The response outcome will be analyzed in a logistic regression model with treatment as the main factor and baseline WOMAC pain as a covariate. Within this model, z-tests will be used to compare the two XT-150 doses to placebo, with step-down Dunnett-like adjustments for multiplicity of doses. Handling of special cases, such as zero responders in a treatment group, will be addressed in the SAP.

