**Treatment Effect That Can Be Detected** 

		Statistical Power (%)		
Placebo response rate (%)	XT-150 response rate (%) in both treatment arms	To detect at least one treatment arm superior to placebo	To detect both treatment arms superior to placebo	
10	25	78	57	
	30	95	85	
	35	99	97	
15	25	38	18	
	30	70	46	
	35	91	77	

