#### 9.4. Adjustment for Multiplicity

Two endpoints will be subject to multiplicity adjustment: The primary endpoint (achievement of a 30% reduction in WOMAC pain)

This will be accomplished by first testing for significance of the two active doses of XT-150 versus placebo with respect to the primary endpoint at the 0.025 level, one-sided. This addresses the multiplicity of doses with respect to the primary endpoint. Then a Dunnett test for the 50% endpoint will be performed at the alpha remaining after having done the first Dunnett test. Using only the remaining alpha for this additional endpoint continues to control the overall false positive rate at 0.025, one-sided. The numerical value of this remaining alpha depends on the primary (30% endpoint) Dunnett test as follows:

[figure not shown]
- If both doses are significantly better than placebo, then the remaining alpha is the full 0.025 level.
- If exactly one of the two active doses is significantly better than placebo, then the alpha remaining will be determined by the software performing the primary Dunnett test. (If the statistical analysis was of Gaussian group means, with N=90 per group, the remaining alpha would be 0.0115 (one-sided); the actual alpha may be different, because the model includes a covariate and the sample sizes may not be exactly 90 per group.)
- If neither active dose is significantly better than placebo, then no alpha remains and no inferential testing will be performed.

Achievement of a 30% improvement in WOMAC Pain score at Day 180 will be analyzed using a logistic regression model as described in Section 9.3 to preserve a familywise error rate of 0.05 (two-sided),

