#### 10. CHANGES FROM THE ANALYSIS PLANNED IN THE PROTOCOL

Although the protocol called for step-down statistical testing using the Dunnett approach, the Dunnett testing will not use step-down testing, because it would exhaust the 'alpha' available for additional statistical testing. By not using the step-down approach, it is permissible to continue statistical testing provided that at least one of the treatment arms is statistically significantly different from the control group, with respect to the primary endpoint.

CONFIDENTIAL Page 20 of 27

Protocol No.: XT-150-2-0204 Sponsor: Xalud Therapeutics, Inc.

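### SAP 4.5 keeps the protocol's 85% power to show both doses superior after SAP 10 drops step-down testing; the SAP's own single-step test gives about 80%

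*SAP*

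**What the plan says.** Protocol 13.5.1 sets the primary analysis to "preserve a familywise error rate of 0.025 (one-sided), accounting for statistical tests of each of the two XT-150 doses to placebo". Protocol 13.5.2 names the test: "z-tests will be used to compare the two XT-150 doses to placebo, with step-down Dunnett-like adjustments for multiplicity of doses". For that plan, Protocol 13.1 claims "85% power to detect both arms superior to placebo, assuming the responder rate is 30% in each XT-150 group" and 10% on placebo. Its Table 7 gives six rows of power for at least one arm and for both arms.

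SAP section 10 changes the test: "the Dunnett testing will not use step-down testing, because it would exhaust the 'alpha' available for additional statistical testing". SAP 9.4 then sets how much alpha passes to a further endpoint. "If both doses are significantly better than placebo, then the remaining alpha is the full 0.025 level". If exactly one dose is significant, the example with Gaussian means and 90 per group says "the remaining alpha would be 0.0115 (one-sided"). If neither is, testing stops.

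SAP 4.5 nevertheless claims "85% power to detect both arms superior to placebo, assuming the WOMAC Pain Score at Day 180 responder rate is 30" per cent on each dose and 10% on placebo. It reprints the whole protocol table, including the column headed "To detect both treatment arms superior to placebo". Neither SAP 4.5 nor Protocol 13.1 names the test behind the table.

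**The concern.** The two rules differ only once one dose has passed. Under step-down, the larger statistic must exceed the Dunnett critical value of about 2.21, and the other then needs only 1.96. Under single-step, both must exceed about 2.21. Power for at least one dose is therefore the same under both rules, while power for both doses must fall when step-down is dropped. A both-arms column left unchanged cannot describe both procedures.

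The SAP thus states a power that its own test does not deliver. The figure is also used: whether both doses or only one succeed decides whether SAP 9.4 passes on 0.025 or about 0.0115. A reader who combines the SAP 4.5 table with the SAP 9.4 rule would expect 85% for the first outcome and 95 − 85 = 10% for the second. Section 10 gives the benefit of the change (alpha left for further tests), but the visible text does not give its cost.

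**Working it through.** **Inputs.** Familywise alpha 0.025 one-sided (Protocol 13.5.1, SAP 9.4); 90 per group, allocated 1:1:1 (SAP 4.5); the response rates in the six table rows; step-down rule (Protocol 13.5.2); single-step rule (SAP 10).

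**Critical value.** With equal groups the two dose-placebo statistics share the placebo arm; take their correlation as 0.5. Solving P(Z₁ ≤ c, Z₂ ≤ c) = 0.975 gives c = 2.2121, with one-sided p = 0.01348. Then 0.025 − 0.01348 = 0.0115, the remaining alpha in SAP 9.4. This confirms that the SAP is working with the single-step test.

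**Power.** Given the placebo count, the two dose arms are independent. Let a = P(Z > 2.2121) and b = P(Z > 1.960) for one dose, given that count, and average over the binomial distribution of the placebo count:

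- at least one: E[1 − (1 − a)²]
- both, step-down: E[b² − (b − a)²]
- both, single-step: E[a²]

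The Wald form is z = (difference in log-odds) / √(1/y₁ + 1/(90 − y₁) + 1/y₀ + 1/(90 − y₀)), where y₁ and y₀ are the responder counts on the dose and on placebo.

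**Plan's own figure, 10% vs 30% (stated: at least one 95, both 85).**

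| Test form | At least one | Both, step-down | Both, single-step | Cost |
|---|---|---|---|---|
| Logistic Wald | 96.2 | 87.5 | 80.4 | 7.1 |
| Pooled z | 96.6 | 87.7 | 82.0 | 5.7 |
| Unpooled z | 96.9 | 88.8 | 82.8 | 6.0 |
| Continuity-corrected z | 94.8 | 83.4 | 75.8 | 7.6 |

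The stated 85 lies inside the step-down range (83.4 to 88.8) and above the whole single-step range (75.8 to 82.8).

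**All rows, both arms.**

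| Placebo / XT-150 (%) | Stated | Wald single-step | Single-step, four forms | Wald cost of dropping step-down |
|---|---|---|---|---|
| 10 / 25 | 57 | 51.0 | 44.2–54.9 | 10.9 |
| 10 / 30 | 85 | 80.4 | 75.8–82.8 | 7.1 |
| 10 / 35 | 97 | 95.0 | 93.4–95.8 | 2.4 |
| 15 / 25 | 18 | 14.3 | 11.0–16.3 | 6.9 |
| 15 / 30 | 46 | 40.4 | 35.1–43.9 | 11.1 |
| 15 / 35 | 77 | 70.6 | 65.8–73.4 | 8.9 |

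All 24 single-step values fall below the stated ones, by 1.2 (97 − 95.8) to 12.8 (57 − 44.2) points.

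**Which rule produced the table?** The gap between its two columns is the chance that exactly one dose succeeds, and this gap separates the rules.

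| Row | Stated gap | Step-down, four forms | Single-step, four forms |
|---|---|---|---|
| 10 / 25 | 78 − 57 = 21 | 19.0–22.3 | 29.2–33.1 |
| 10 / 30 | 95 − 85 = 10 | 8.1–11.4 | 14.1–19.0 |
| 10 / 35 | 99 − 97 = 2 | 1.9–3.2 | 3.8–5.9 |
| 15 / 25 | 38 − 18 = 20 | 19.9–22.1 | 25.4–28.9 |
| 15 / 30 | 70 − 46 = 24 | 22.0–24.2 | 32.2–33.7 |
| 15 / 35 | 91 − 77 = 14 | 12.5–15.7 | 20.0–24.3 |

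Every stated gap fits step-down and none fits single-step.

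**Consequence for SAP 9.4 at 10% vs 30%, Wald single-step.** Both doses 80.4%, exactly one 15.7%, neither 3.8%, against 85%, 10% and 5% read from the table.

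**Covariate.** In simulations of the adjusted logistic model, single-step power for both doses was 81.2, 81.3 and 82.9% for assumed baseline effects of 0, 0.3 and 0.5 log-odds per SD (12,000 runs each, Monte Carlo SE 0.4). A separate 10,000-run simulation with no baseline effect gave 80.5%. The documents give no covariate effect, so these effects are assumptions.

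**The case against.** The strongest reply is that setting 85 against 80 is not like for like. The Wald method gives 87.5% under step-down, so it does not reproduce the sponsor's 85% either. Only the continuity-corrected form comes near the whole table at 90 per group (largest error 2.6 points under step-down, 12.8 under single-step). This stands. The cost of the change itself is 87.5 to 80.4 by Wald, or 83.4 to 75.8 with the continuity correction: about 7 points either way. It does not rescue the 85%, which no form reaches under single-step.

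Second, 2.21 is an approximation. SAP 9.4 leaves the actual value to the software. At 10% vs 30% the log-odds variances are 1/(90 × 0.09) = 0.123 for placebo and 1/(90 × 0.21) = 0.053 for a dose, so the two contrasts correlate at 0.123/0.176 = 0.70. The critical value is then about 2.18. Estimating the correlation from each dataset raises the Wald figure to 81.4%, still short of 85%.

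Third, the link between the table and step-down is inferred, since no test is named. That is so, but the error does not depend on it: the figure is wrong for the SAP's test however it was derived.

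Fourth, the branch with reduced alpha does not exist under step-down, so 85/10 and 80/16 do not compare two versions of one procedure. This is correct. They compare what the SAP's table implies with what the SAP's test does.

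Fifth, section 10 discloses the change of test, and this is a modest correction to one power statement. The disclosure does not extend to the loss of power. The size is indeed modest.

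**Conclusion.** The concern holds. The 85% and the both-arms column in SAP 4.5 do not describe the test in SAP section 10. At 90 per group and 10% vs 30%, power to show both doses superior is about 80% by the logistic Wald test. It is 76% to 83% across the four test forms, and about 81% to 83% in the simulations with an assumed baseline effect. The loss from dropping step-down is about 7 points by the Wald test at the design assumption (5.7 to 7.6 over test forms) and 2 to 11 across the rows. These figures assume 90 analysed per group, missing Day 180 responses already reflected in the response rates, and, for the exact calculations, a correlation of 0.5.

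The claim of more than 90% power for at least one dose stands. Sample size, type I error control and the choice of test are not in question. This should be corrected, but it does not threaten the primary analysis.

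**What to change.** In SAP 4.5, recompute both columns for the single-step Dunnett test of section 10 by one named method, and replace 85% with the result, about 80%. With the Wald test at 90 per group, in table order, both arms is about 51, 80, 95, 14, 40 and 71%, and at least one arm about 82, 96, 99.5, 42, 73 and 92.5%. If the sponsor can recover the method behind the existing table, a smaller change is enough: keep the at-least-one column, recompute only the both-arms column by that method, and name it. Either way, the two columns must come from the same calculation.

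In section 10, add that dropping step-down costs about 7 points of power to show both doses superior at the design assumption, and 2 to 11 across the table.

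The cost is one sentence and one table in SAP 4.5 and one sentence in section 10. The only drawback is a less favourable stated figure. No extra patients and no change of test or alpha are needed.

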**Treatment Effect That Can Be Detected** 

		Statistical Power (%)		
Placebo response rate (%)	XT-150 response rate (%) in both treatment arms	To detect at least one treatment arm superior to placebo	To detect both treatment arms superior to placebo	
10	25	78	57	
	30	95	85	
	35	99	97	
15	25	38	18	
	30	70	46	
	35	91	77	

#### 4.6. Study Endpoints

#### Safety.

Safety measures to be assessed throughout the study from signing of the informed consent form (ICF).

CONFIDENTIAL Page 9 of 27

Protocol No.: XT-150-2-0204 Sponsor: Xalud Therapeutics, Inc.

- Vital signs (temperature and the collection site [i.e., oral, rectal, temporal, or tympanic], heart rate, blood pressure, and respiratory rate)
- Physical examination including all major organ systems
- Injection site examination

Safety assessments conducted after completion of the study by all participants include serum assay results for anti-IL-10 antibody.

[figure not shown]
#### Efficacy:

The primary efficacy outcome measure is whether the subject achieves at least a 30% improvement from baseline in WOMAC Pain Score (obtained from the KOOS questionnaire) at Day 180, as recorded on a 0 to 20 point scale with 20 being the maximum (worst) score.

Secondary efficacy outcome measures are:

- Change from baseline in the WOMAC Function Score (from KOOS questionnaire) at Day 180
- Change from baseline in the WOMAC Pain Score (from KOOS questionnaire) at Day 180 (this endpoint was inadvertently omitted from the protocol)
- Change from baseline in patient response at Day 180, using a scale of 1 5, to the
  OA question: "Considering all the ways the OA in your knee affects you, how are
  you doing today?", with 1 being very good (asymptomatic and no limitation of
  normal activities) to 5, very poor (very severe, intolerable symptoms and inability
  to carry out normal activities)

Additional endpoints include:

CONFIDENTIAL Page 10 of 27

Final 2.0, 11 Oct 2021

Protocol No.: XT-150-2-0204 Sponsor: Xalud Therapeutics, Inc.

[figure not shown]

#### 5. DATA LISTINGS

#### 5.1. Sources of Data

Data sets containing raw data will be provided by the Data Management group, extracted from the clinical study database of data entered into a Case Report Form. The clinical study database will contain the data from Screening through to the Follow-up Safety Visit of the study.

Data sets (SDTM and ADaM) will be generated from the clinical study database of data entered into a Case Report Form, along with the following data received from other sources:

All data entered into the CRF or provided from other sources as described above will be presented (explicitly or implicitly) in data listings or figures as described in Appendix 1.

#### 5.2. Randomization and Subject Identification Code

After informed consent has been obtained, participants will be screened for study eligibility before enrollment. A total of 270 subjects will be randomized to the following 6 treatment sequences in a 1:1:1:1:1 ratio:

- XT-150 (150 μg) in Stage A, followed by XT-150 (150 μg) in Stage B
- XT-150 (150 μg) in Stage A, followed by XT-150 (450 μg) in Stage B
- XT-150 (450 μg) in Stage A, followed by XT-150 (150 μg) in Stage B
- XT-150 (450 μg) in Stage A, followed by XT-150 (450 μg) in Stage B
- Placebo in Stage A, followed by XT-150 (150 μg) in Stage B
- Placebo in Stage A, followed by XT-150 (450 μg) in Stage B

The randomization schedule will be prepared by unblinded statisticians using SAS version 9.4 (or higher) statistical software package and will be maintained under controlled access. A copy of the randomization schedule will be provided to unblinded site pharmacy staff for the purposes of dispensing the study drugs.

CONFIDENTIAL Page 11 of 27

Protocol No.: XT-150-2-0204 Sponsor: Xalud Therapeutics, Inc.

Subjects will be assigned a randomisation number with the format 'Rnnn', where 'nnn' is the sequential subject id, from 001 to 270.

In the listings, subjects will be identified by randomisation number, with dose of XT-150 (treatment) as a secondary grouping identifier. Screening number will be shown only on the listing of informed consent data.

#### 5.3. Maintaining the Study Blind

In this double-blind study, all personnel involved, i.e., physicians, site staff, and participants will remain blinded at all times, except in an emergency where knowledge of the randomisation code is required to provide appropriate treatment for an adverse event. The Investigator has the sole responsibility for determining if unblinding of a subject's treatment assignment is warranted for emergency reasons.

Preparation of the randomisation schedule in was performed by staff members who have no responsibility for monitoring and data management of this study.

The listings for inclusion in an appendix to the report will be prepared after the database has been locked and the study has been unblinded.

